3 STUDY OBJECTIVES & ENDPOINTS

3.1 Study Objectives & Hypothesis

3.1.1 Primary Objective & Hypothesis

- Objective: To assess the safety and tolerability of SBRT in MPM with pembrolizumab.
- Hypothesis: SBRT in MPM can be safely administered in combination with pembrolizumab without significant dose limiting acute toxicity.

3.1.2 Secondary Objectives

- To describe the safety profile of SBRT in MPM in combination with pembrolizumab.
- To assess clinical benefit with overall responses rate (ORR), disease control rate (DCR) and duration of response (DOR).
- To assess responses rates in epithelioid versus sarcomatoid histological subtypes of MPM.
- To assess response rates in relation to tumour PD-1/PD-L1 expression.
- To assess progression free survival (PFS) and overall survival (OS).

3.1.3 Exploratory Objectives

- To identify biomarkers that correlate with immunological response to therapy.
- To analyse peripheral blood samples for ctDNA.

3.2 Study Endpoints

3.2.1 Primary Endpoint

- To assess the dose limiting toxicity (DLT) of SBRT in MPM at a dose level of 30 Gy given in 3 fractions when combined with pembrolizumab.

3.2.2 Secondary Endpoints

- To assess acute toxicity rates (defined as up to 12 weeks after last SBRT fraction) using CTC AE v5.0.
- To assess late toxicity rates (defined as from 12 weeks after last SBRT fraction in MPM until 28 days after the last dose of pembrolizumab) using CTCAE version 5.0.
- To calculate the ORR, DCR and DOR using mRECIST and RESIST 1.1.
- To calculate the ORR and DCR in epithelioid versus sarcomatoid histological subtype using mRECIST and RESIST 1.1.
- To assess the frequency of PD-1/PD-L1 expression distribution in responders and non-responders.
- To measure the PFS and OS at 6 and 12 months.

3.2.3 Exploratory Endpoints

- To characterise tumour infiltrating lymphocytes and tumour antigens in the tumour biopsies. These immunohistochemistry analyses will include, but not necessarily be limited to, the following markers: CD4, CD8, FOXP3, PD-1, PD-L1, and PD-L2.

- To assess for levels of ctDNA pre- and post- SBRT.

4 STUDY DESIGN

4.1 Summary of Study Design

This is a non-randomised open-label phase 1 trial of pembrolizumab given in combination with SBRT to part of a pleural-based lesion in patients with unresectable MPM. This study will recruit up to 18 patients whose MPM has progressed beyond first-line of palliative chemotherapy, with a platinum-based doublet, and now requires further palliative systemic treatment, or have declined first-line palliative chemotherapy, however must have been considered suitable for a platinum doublet chemotherapy.

4.2 Treatment Regimen

The study will be conducted in two parts; an initial safety phase (Part A), followed by an expansion cohort (Part B). The initial safety phase (Part A) is based on a 3+3 design such that patients will be treated in a cohort of 3-6 patients. A maximum of 6 patients will be allocated to Part A exploring SBRT 30 Gy in 3 fractions in combination with pembrolizumab. If there is more than one DLT in the first 3 patients or two or more DLTs in the first 6 patients, this treatment combination will be deemed as being unacceptable and it would lead to termination of the study. During the expansion cohort (Part B), 12 patients will have SBRT 30 Gy in 3 fractions with pembrolizumab to obtain additional safety and response data. Maintenance pembrolizumab will continue until disease progression, unacceptable toxicities, the patient withdraws consent to the trial, or the patient has completed 35 cycles of treatment. A maximum of 18 patients will be treated in the study.

All patients will receive pembrolizumab on cycle (C) 1 day (D) 1, in Part A and B of the study. All patients will receive SBRT on C1D15, C1D17 and C1D19, as per SBRT protocol (See Appendix 3). Patients in part A will receive SBRT 30 Gy in 3#. Patients in Part B will receive 30 Gy in 3 fractions if considered safe after part A. All patients in Part A and Part B will receive pembrolizumab dosed at 200 mg every 3 weeks, until disease progression, unacceptable toxicities, the patient withdraws consent from the trial or the patient has completed 35 cycles of treatment.

In the initial safety cohort, a minimum of 3 patients will be treated at the SBRT dose of 30Gy in 3 fractions combined with pembrolizumab. The gap left between the treatments of each subsequent patient will start after the second cycle of Pembrolizumab in the previous dosed patient to mitigate against multiple patients suffering from acute toxicity. The DLT period for this study is 12 weeks from the last dose of SBRT (i.e. at C6D1). Patients included in Part A will be considered by the Safety Review Committee (SRC) once the 3rd and 6th patient in the Part A cohort has completed the DLT period. If 0 out of 3 patients experience a DLT, or if 1 out of 3 patients experience a DLT in Part A, then the cohort will be expanded to 6 patients. If 1 in 6 patients experience a DLT, then it will be acceptable to move forward to the expansion cohort (Part B). However, if ≥ 2 in 6 patients (or more than 1 in the first 3 patients) experience a DLT then the maximum administered dose

(MAD) will have been reached. If the MAD is seen at a dose level of 30 Gy in 3# then the study will be terminated.

While waiting for 3 or 6 patients to complete the DLT period, no additional patients will be recruited. Further patients can only be recruited after the SRC has reviewed the toxicity data for the cohort to proceed to Part B. Patients obtaining complete response or having completed 35 cycles of pembrolizumab must discontinue and may recommence for additional 17 cycles upon subsequent disease, the CI/PI will need to discuss with the sponsor and MSD, on a case by case basis for the continuation of pembrolizumab.

Table 1: SBRT dose level and pembrolizumab dosing during the initial safety cohort and expansion phase.

Dose Level	Pembrolizumab Dose	SBRT to part of a MPM lesion
Initial safety cohort	200 mg i.v. over 30 minutes, every 3 weeks	30 Gy in 3# (Monday, Wednesday, Friday)
Expansion cohort	200 mg i.v. over 30 minutes, every 3 weeks	30 Gy in 3# (Monday, Wednesday, Friday)

SBRT: Stereotactic Ablative Body Radiotherapy; Gy: Gray; i.v.: intravenous; mg: milligrams; #: fraction.

4.2.1 Dose Limiting Toxicities

Acute toxicity will be assessed up to and including 3 months following the final fraction of radiotherapy (i.e. at C6D1). The MRC dyspnoea score (Appendix 2) will be used to assess dyspnoea at baseline/on treatment and the Common Toxicity Criteria for Adverse Events (CTCAE) version 5.0 will be used to grade all drug and SBRT observed toxicities (Appendix 4). The SRC will consider expansion after the 6th patient in the initial safety cohort has completed the DLT period and reviewed the toxicities before recruitment to the expansion cohort Part B.

Any DLT must be a toxicity that is considered probably, possibly or definitely related to the combination of pembrolizumab and SBRT. DLT is defined as follows:

Haematologic:

- Neutropenia with fever grade 3 or neutropenia grade 4
- Thrombocytopenia with bleeding grade 3 or thrombocytopenia grade 4

Non-Haematologic:

Any ≥ 3 non-haematological toxicity which is definitely, probably or possibly related to the combination of pembrolizumab and SBRT for pleural mesothelioma including the following:

- Increased MRC dyspnoea score > 2 grades from baseline and/or acute dyspnoea grade ≥ 4 (or CTCAE dyspnoea grade ≥ 3) persisting for > 7 days (including weekend).
- Pneumonitis grade ≥ 3 persisting for > 7 days (including weekend).
- Oesophagitis grade ≥ 3 persisting for > 7 days (including weekend).
- Toxicity leading to interruption of radiotherapy for > 7 days (including weekend).

Progression of the study will not proceed until the following criteria are satisfied by the SRC:

- If 0 out of 3 patients experience a DLT, or if 1 out of 3 patients experience a DLT, a further 3 patients will be recruited at the dose level in the initial safety cohort.
 - If 0 out of 6 patients experience a DLT, or if 1 out of 6 patients experience a DLT, then progression to Part B of the study can proceed.
 - If ≥ 2 out of 6 patients (or more than 1 in the first 3 patients) experience a DLT, then there will be no Part B expansion phase and the study will be terminated.

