4.5.1 Clinical Criteria for Early Trial Termination

Early trial termination will be the result of the criteria specified below:

1. Quality or quantity of data recording is inaccurate or incomplete
2. Poor adherence to protocol and regulatory requirements
3. Incidence or severity of adverse drug reaction in this or other studies indicates a potential health hazard to patients
4. Plans to modify or discontinue the development of the study drug
5. If DLT is seen in Part A in 2 out of 3 or 2 out of 6 patients.

In accordance with the conditions of supply agreement with MSD, ample notification will be provided to the sponsor (via RM-CTU) and sites should alterations to the drug supply change. This is to allow time for appropriate adjustments to be made in regards to the patient's treatment.

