5.3 Patient Replacement Strategy

Additional patients may be enrolled in a given cohort to ensure that the required number of evaluable patients in each cohort is achieved. A patient that discontinues the trial for progressive disease within 3 months of the last dose of radiotherapy will not be evaluable for DLTs and therefore will need to be replaced. A patient that discontinues the trial for a drug-related AE will not be replaced and will be counted in the evaluable population of patients for the respective cohort. However, patients found to have active pneumonitis on C1D1 of pembrolizumab or day 1 of radiotherapy will be removed from the trial and can be replaced. Also patients who

do not reach follow-up 3 months post completion of SBRT for MPM for reasons other than progression or toxicity can be replaced by new patients in that cohort to ensure there is a minimum of 3 (or 6 if required) patients in each cohort.

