irAE	Withhold/Discontinue Pembrolizumab?	Supportive Care
Grade 1	No action	Provide symptomatic treatment
Grade 2	May withhold pembrolizumab. For recurrent grade 2 pneumonitis, pembrolizumab should be discontinued permanently.	Consider systemic corticosteroids in addition to appropriate symptomatic treatment. Steroid taper should be considered once symptoms improve to Grade 1 or less and tapered over at least 4 weeks. Based on limited data from clinical studies in subjects whose immune-related adverse reactions could not be controlled with corticosteroid use, administration of other systemic immunosuppressants can be considered.
Grade 3 and Grade 4	Withhold pembrolizumab Discontinue if unable to reduce corticosteroid dose to < 10 mg per day prednisone equivalent within 12 weeks of toxicity	Systemic corticosteroids are indicated in addition to appropriate symptomatic treatment. May utilize 1 to 2 mg/kg prednisone or equivalent per day. Steroid taper should be considered once symptoms improve to Grade 1 or less and tapered over at least 4 weeks. Based on limited data from clinical studies in subjects whose immune-related adverse reactions could not be controlled with corticosteroid use, administration of other systemic immunosuppressants can be considered.
Please Note: If an irAE does not resolve or improve to \leq Grade 1 within 12 weeks after last administration of pembrolizumab, study therapy discontinuation should be considered after discussion with a Merck Clinical Director via the RM-CTU trial manager.		

Details for managing specific irAEs are summarised below:

Immune-mediated pneumonitis

Monitor subjects for signs and symptoms of pneumonitis. If pneumonitis is suspected, evaluate with radiographic imaging and exclude other causes. Administer corticosteroids for Grade 2 or greater events (initial dose of 1-2 mg/kg/day prednisone or equivalent followed by a taper), withhold pembrolizumab for moderate (Grade 2) pneumonitis, and permanently discontinue pembrolizumab for recurrent moderate (Grade 2), severe (Grade 3) or life-threatening (Grade 4) pneumonitis.

Immune-mediated colitis

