8.2 Assessing and Recording Adverse Events

All AEs will be recorded from the time of the first dose until the safety follow-up in the CRF. They will be followed up according to local practice until the event has stabilised or resolved, or the follow-up visit has taken place, whichever is the sooner. SAEs will also be recorded throughout the study. The reporting timeframe for AEs meeting any serious criteria is described in section 8.4.

Follow-up of AEs with a causality of possible, probable or highly probable will continue until the events resolve, stabilise or the patient completes the trial. Any unresolved AEs at the patient's last visit should be followed up for as long as medically indicated, but without further recording in the CRF.

If an Investigator learns of any AE that he/she consider serious, including death, at any time after a patient has completed the study and he/she considers there is a reasonable possibility that the event is related to pembrolizumab, the Investigator should notify the RM-CTU. Late toxicities will be recorded and reported as with other AEs.

The following details will be collected in the CRF for each AE:

- AE description / diagnosis
- Date of onset and date of resolution
- CTCAE grade maximum intensity
- Seriousness
- Investigator causality rating against the study medication (yes or no)
- Expectedness
- Action taken with regard to study medication
- Outcome

For the pre-registration period AEs will not be collected in patients that have not undergone any protocol-specified procedure or intervention. If the patient requires a blood draw, fresh tumour biopsy etc. for the study then the patient will be required to consent to the main study and AEs will be captured as described above.

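### Section 4.2.1 gives two DLT tests for related grade ≥3 pneumonitis, oesophagitis and dyspnoea lasting 7 days or less, so the same Part A data can mean stop or continue

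*Protocol*

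**What the plan says.** Section 4.2.1 defines the DLT. For non-haematological events it opens with a general clause: "Any ≥ 3 non-haematological toxicity which is definitely, probably or possibly related to the combination of pembrolizumab and SBRT". The word 'grade' is missing, but the section grades toxicity by CTCAE version 5.0, so CTCAE grade ≥3 is evidently meant. The clause carries no duration condition.

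The clause then introduces a list with the word 'including'. Three entries repeat the grade threshold and add a duration:

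- "Pneumonitis grade ≥ 3 persisting for > 7 days (including weekend"
- "Oesophagitis grade ≥ 3 persisting for > 7 days (including weekend"
- for dyspnoea, "or CTCAE dyspnoea grade ≥ 3) persisting for > 7 days (including weekend"

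The decision rule in Sections 4.2 and 4.2.1 works on the number of patients with a DLT. With 0 or 1 of the first 3, three more are recruited. With 0 or 1 of 6, Part B may open. With more than 1 of the first 3, or 2 or more of 6, the study ends. Section 4.5.1 lists the same trigger among the reasons for early termination: "If DLT is seen in Part A in 2 out of 3 or 2 out of 6 patients". Section 9.1.1 reports the Part A DLT proportion with an exact binomial confidence interval as the primary result.

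**The concern.** Take a related grade 3 pneumonitis that falls below grade 3 after 5 days. Under the general clause it is a DLT. Under the only line that names pneumonitis it is not. If the general clause governs, the more-than-7-days condition on these three CTCAE criteria has no effect. If the list governs, the word 'Any' is wrong for these three events. No wording such as 'except' or 'unless' settles the order, and Sections 4.2, 4.5.1, 9.1.1 and 9.1.4 use the DLT count without resolving it.

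The Safety Review Committee applies the count during an open-label trial, and its members include the Chief Investigator and Co-Investigators (Section 11.9). As written, it would have to choose a reading of the primary endpoint after seeing the events. That choice can decide whether the trial stops or 12 more patients are treated.

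The point is confined to these three event types at CTCAE grade ≥3 lasting 7 days or less. The MRC-score criterion, the radiotherapy-interruption criterion, longer events and all other related grade ≥3 non-haematological events are not in question.

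**Working it through.** **Inputs.** Part A has 3 to 6 patients and Part B 12 (Section 9.2). The plan's stated maximum is reproduced: 6 + 12 = 18. The protocol states no target DLT rate, alpha or power for the rule, so there is no operating characteristic to reproduce.

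**Classification of one related grade ≥3 event (pneumonitis, oesophagitis or CTCAE dyspnoea).**

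| Time at grade ≥3 | General clause | List entry |
|---|---|---|
| More than 7 days | DLT | DLT |
| 7 days or less | DLT | not a DLT |

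Only the second row is in dispute.

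**Denominator.** Replacement does not absorb the difference. Section 5.3 says "A patient that discontinues the trial for a drug-related AE will not be replaced and will be counted in the evaluable population", and a patient who stops the drug but stays in follow-up is also evaluable. The section does allow replacement for pneumonitis already active on C1D1 or on radiotherapy day 1. The examples assume later onset and no other unevaluable patients, so the denominator is the same on both readings.

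**Same data, two results.** The interval is Clopper-Pearson. For x of n, the lower limit is the 2.5% quantile of Beta(x, n−x+1) and the upper limit is the 97.5% quantile of Beta(x+1, n−x). For x = 0 the lower limit is 0 and the upper limit is 1 − 0.025^(1/n): 70.8% for n = 3 and 45.9% for n = 6.

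| Data | General clause governs | List governs |
|---|---|---|
| Two 5-day grade 3 pneumonitis events in the first 3 patients | 2/3 = 66.7% (9.4 to 99.2%): terminate | 0/3 = 0% (0 to 70.8%): recruit 3 more |
| Two such events in 6, one in each group of 3 | 2/6 = 33.3% (4.3 to 77.7%): terminate | 0/6 = 0% (0 to 45.9%): may proceed |
| One such event plus one undisputed DLT, one in each group of 3 | 2/6 = 33.3% (4.3 to 77.7%): terminate | 1/6 = 16.7% (0.4 to 64.1%): may proceed |

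In the third row a single disputed event changes the outcome.

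**Illustration under assumed rates.** More than 1 DLT in the first 3 patients already means at least 2 in 6. The probability of termination at a per-patient DLT rate p is therefore 1 − (1−p)^6 − 6p(1−p)^5. At p = 0.10 this is 1 − 0.531 − 0.354 = 0.114. Let p be the DLT rate when the list governs. Let s be the added proportion of patients whose only qualifying event is a disputed short one. Neither figure is in the protocol, so both are assumed.

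| p (list governs) | P(terminate) at p | at p + 5% | at p + 10% | at p + 20% |
|---|---|---|---|---|
| 5% | 0.033 | 0.114 | 0.224 | 0.466 |
| 10% | 0.114 | 0.224 | 0.345 | 0.580 |
| 20% | 0.345 | 0.466 | 0.580 | 0.767 |

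**Other sections.** The management text does not settle the question. Section 7.5 says to "permanently discontinue pembrolizumab for recurrent moderate (Grade 2), severe (Grade 3) or life-threatening (Grade 4) pneumonitis", and Table 8 agrees for grades 3 and 4; neither sets a duration. On the list reading, an event can end a patient's pembrolizumab without counting as a DLT. That is not in itself a contradiction, because stopping rules and DLT definitions serve different purposes, but it gives no help in choosing a reading.

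**The case against.** The best reply is that 'including' ordinarily introduces examples and does not narrow 'Any'. The list entries would then be sufficient conditions only, a 5-day grade 3 pneumonitis would be a DLT, and the fault would be redundancy. This reading is available, and on it there is no strict logical contradiction. It leaves three duration conditions without any effect, however, and they gain meaning only if they narrow the general clause. Both readings are reasonable, which a go/no-go endpoint cannot afford.

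A second reply is that the go rule is permissive. Part B can open but need not, the committee sees all serious events, and Section 4.5.1 separately allows termination for the incidence or severity of adverse drug reactions. This stands for the review after 6 patients, so the result there is that the trial may proceed. It does not hold at the first review, where 2/3 requires termination and 0/3 leads to three more patients. Nor do these safeguards settle the DLT proportion reported under Section 9.1.1.

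Third, the trigger is narrow and its frequency unknown. Appendix 3 excludes central lesions and sets a mandatory oesophageal dose constraint, which bears on oesophagitis. That is fair, and no likelihood is claimed. The event types are still foreseeable: Section 7.1.2 names pneumonitis and oesophagitis for recording, and Table 3 schedules chest X-rays in the DLT period to monitor for pneumonitis.

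**Conclusion.** The concern holds. The primary endpoint has two readings for one defined class of events, and the protocol does not choose between them. On identical data the readings can give 2/3 against 0/3 at the first review, and 2/6 against 0/6 or 1/6 at the second, with opposite results under the stopping rule and different primary estimates. The examples rest on the assumptions that the general clause means CTCAE grade, that the events are judged related to the combination, and that all patients are evaluable. The finding does not depend on any assumed event rate. It must be fixed before the rule is applied.

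**What to change.** Reconcile the general clause and the list in Section 4.2.1 so that every event has exactly one DLT classification. Which threshold to keep is for the sponsor to decide. The choice should be fixed in writing before the first Safety Review Committee review of DLT data, after the 3rd patient completes the DLT period, and the same definition should be used for the proportion in Section 9.1.1.

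The cost is protocol wording. Sample size and data collection do not change. Section 8.2 already collects "Date of onset and date of resolution", and Section 8.3.1 opens a new record at each change of grade, so time at grade ≥3 can be derived on either definition. The reported DLT rate and the go/no-go result may depend on the definition kept.

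A minor point for the same amendment: Sections 8.2 and 8.3.2 word causality mainly against the study drug, while Section 4.2.1 words it against the combination with SBRT. Aligning them would help, but the finding does not rest on it.

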4.3 Study Schema

[figure not shown]

Figure 1: Schematic diagram of study events. Patients will receive pembrolizumab dosed at 200 mg i.v. every 3 weeks (as indicated by ▼). SBRT for pleural mesothelioma will be administered on cycle 1 days 15, 17 and 19 (as indicated by ■).

4.4 Follow-Up after stopping Pembrolizumab

4.4.1 30 Day Safety Follow-Up Visit

All patients will be required to attend a safety follow-up visit 30 days after the last dose of pembrolizumab or before the initiation of a new anti-cancer treatment, whichever comes first. Patients who restart treatment on disease progression, once completed the treatment period will also attend to a safety follow-up visit as detailed above. All adverse events (AEs) and serious adverse events (SAEs) that occur prior to the safety follow-up visit should be reported as described in section 8. After the safety follow-up any unresolved AEs at the patient's last visit should be followed up for as long as medically indicated, but without further recording in the CRF.

4.4.2 Follow-Up for Discontinued Pembrolizumab without Disease Progression

Patients who discontinue pembrolizumab for any reason other than disease progression will move into the follow-up phase and should be assessed every 9 weeks (63 ± 7 days) and by radiologic imaging as per standard of care to monitor disease status. Every effort should be made to collect information regarding disease status

until the start of new anti-cancer therapy, disease progression, death, withdrawal or end of the study. Information regarding post-study anti-cancer treatment will be collected if new treatment is initiated.

